5.7.2 Secondary endpoints

All secondary efficacy variables will be analyzed based on the FAS and additionally on the PP population if these populations differ by $>5\%$. In case of surgical endpoints, the analysis will be based on the SURG set (refer to section 5.9) and for PK parameters on the PK set (refer to section 5.8).

Secondary endpoints are:

- Spontaneous annualized bleeding rate (SABR), calculated in analogy with TABR
- Efficacy of *Wilate* in the treatment of breakthrough BEs based on the proportion of BEs successfully treated with *Wilate* (successfully includes efficacy ratings assessed as either 'excellent' or 'good')
- *Wilate* consumption data (FVIII IU/kg per week per subject) for prophylaxis
- Baseline PK parameters for FVIII:C using both the chromogenic (CHR) and one-stage (OS) assays and actual IMP potencies (for details see section 5.8)

STATISTICAL ANALYSIS PLAN

Protocol No: WIL-27

Version Number: 5.0

Date of Issue: 2018-05-08

Page 20 of 27

- Incremental IVR of *Wilate* over time (at baseline, and at 3 and 6 months of treatment)
- Association between ABO blood type and the FVIII:C half-life of *Wilate*
- Association between VWF:Ag concentration and the FVIII:C half-life of *Wilate*
- Safety and tolerability of *Wilate* by monitoring adverse events (AEs) throughout the study (for details see section 5.10.1)
- Immunogenicity of *Wilate* by testing for FVIII inhibitors (for details see section 5.10.3)
- Virus safety in terms of parvovirus B19 (for details see section 5.10.3)

The secondary endpoint SABR will be analyzed in complete analogy to the TABR, the only exception being that, for the comparison of mean SABRs, a predefined threshold of 19.1 per subject per year is chosen; this threshold corresponds to 50% of the SABR reported in GENA-01.

If μ' denotes the mean SABR, then the following pair of hypotheses will be tested:

$$H_0: \mu' \geq 19.1 \text{ vs. } H_1: \mu' < 19.1$$

In addition to the comparison of the subjects' ABR to the defined thresholds derived from GENA-01, intra-individual comparisons with each subject's documented pre-study ABR (based on bleedings documented for at least 6 months prior to study start) will be performed. For this, descriptive statistics for pre-study and current ABRs and their intra-individual differences will be presented, and the matched-pairs signed rank test ($\alpha = 5\%$) will be used to test for a shift in ABR distributions.

Regarding efficacy in the treatment of breakthrough BEs, confirmatory statistical testing will test the null hypotheses that the percentage of success is $\leq 70\%$ (alternative hypothesis: percentage $> 70\%$); the test procedure based on the generalized estimation equation will take into account several BEs in one subject as correlated repeated measurements.

Thus, if π denotes the proportion of success, then the following pair of hypotheses will be tested:

$$H_0: \pi \leq 0.7 \text{ vs. } H_1: \pi > 0.7$$

The statistical analysis of other secondary endpoints will be descriptive, including exploratory 95% confidence intervals for the location parameters.

In general, the efficacy of bleeding episodes will also be presented by type (spontaneous, traumatic, postoperative, other), sites (Nose, oral cavity, knee, ankle, elbow, arm, leg, intestinal and other. In addition, knee, ankle and elbow sites will be summarized as site 'joint') and severity (minor, moderate, major, life-threatening).

STATISTICAL ANALYSIS PLAN Protocol No: WIL-27	
Version Number: 5.0	Page 21 of 27
Date of Issue: 2018-05-08	

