5 STATISTICAL ANALYSES

All statistical analyses will be performed using SAS® for Windows (Version 9.3 or later).

Descriptive statistics will always be given for the entire population.

The analysis of safety will be based on the SAF set.

The evaluation of the primary endpoint will be performed on the FAS (ITT analysis) and on the PP set (PP analysis).

STATISTICAL ANALYSIS PLAN Protocol No: WIL-27
	
Version Number: 5.0	Page 16 of 27
Date of Issue: 2018-05-08	

For secondary endpoints, ITT and PP analyses will be carried out, unless these analysis sets differ by no more than 5% of subjects in the FAS.

Analysis of the PK properties of *Wilate* will be based on the PK set.

Analysis of the efficacy and safety of *Wilate* in surgeries will be based on the SURG set.

If not stated otherwise the following standard descriptive statistics will be presented:

Descriptive statistics for continuous data

Number of subjects (N), arithmetic mean, standard deviation (SD), minimum, lower quartile, median, upper quartile and maximum will be presented. Usually mean and quartiles will have 1 decimal more, SD 2 decimals more than the original values (as given with min, max); N has no decimals. These descriptive statistics will be determined for measured values and for differences to baseline.

Descriptive statistics for categorical data

Absolute frequencies (N) will be presented with 0, relative frequencies (%) with 1 or 2 decimals, as applicable. For changes from baseline, shift tables may be generated.

Inferential statistics

If not stated otherwise all statistical tests will be performed as described in the corresponding sections below.

All p-values will be rounded to 4 decimals (p<0.0001 will be displayed, if the p-values are less than 0.0001). Statistical significance will be declared if the rounded p-value will be less than 0.050.

All confidence intervals (CI) will be derived two-sided and at a confidence probability of $1 - \alpha = 0.95$.

Listings

All subject data will be listed by subject. Identification variable will be the subject ID (composed of study, center and subject number separated by a hyphen, e.g. '27-01-01'). Any derived data listed will also be stored permanently and will be calculated as outlined in section 8.1 of this SAP.

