5.7.1 Primary endpoint

The primary endpoint of this study is a 50% reduction of the total annualized bleeding rate (TABR) observed in the GENA-01 study with a total of 58.1 BEs per subject per year.

The efficacy of prophylactic treatment with *Wilate* will be statistically evaluated by comparing the primary endpoint, i.e., TABR under prophylaxis, with a predefined threshold of 29 per subject per year. This threshold corresponds to 50% of the TABR reported in GENA-01, a study in which previously treated adolescent and adult subjects with severe hemophilia A received on-demand FVIII treatment only.

TABR will be calculated as the total number of BEs in the time period between first dose of IMP and the Study Completion Visit, divided by the duration (in years) between first dose of IMP and the Study Completion Visit. Surgery periods, and BEs occurring within these periods, will be excluded from the calculation of TABR.

A confirmative one-sided, one-sample Poisson-test will be used to test whether the mean TABR in subjects treated prophylactically with *Wilate* is below the threshold of 29 BEs per subject year ($\alpha = 2.5\%$). A corresponding two-sided 95% CI for the TABR will also be provided.

If μ denotes the mean TABR, then the following pair of hypotheses will be tested:

$$H_0: \mu \geq 29 \text{ vs. } H_1: \mu < 29$$

The null hypothesis will be rejected (at a one-sided alpha level of 2.5%) if the upper limit of the one-sided 97.5% confidence interval for μ is strictly less than 29.

This mentioned confidence interval will be derived from a generalized linear model with a Poisson error, log-link function and log (exposure time) as offset term.

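### SABR and bleed-treatment success are tested as confirmatory with no order, alpha split or condition on the primary, and no deciding analysis set is named for TABR

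*SAP*

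**What the plan says.** **TABR (primary).** SAP 5.7.1: "A confirmative one-sided, one-sample Poisson-test will be used to test whether the mean TABR" is below 29 per subject-year. The level is explicit: "The null hypothesis will be rejected (at a one-sided alpha level of 2.5"%, one-sided. Protocol 9.2.2 says the same.

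**SABR (secondary).** SAP 5.7.2: "The secondary endpoint SABR will be analyzed in complete analogy to the TABR, the only exception being that" the threshold differs: "a predefined threshold of 19.1 per subject per year is chosen". SABR has its own pair of hypotheses. It is not itself labelled confirmatory; that status follows from the analogy.

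**Bleed-treatment success (secondary).** SAP 5.7.2: "Regarding efficacy in the treatment of breakthrough BEs, confirmatory statistical testing will test the null hypotheses that the percentage of success is" at most 70%, using generalized estimating equations. Protocol 9.2.2 and the synopsis also call this confirmatory. An alpha of 2.5% for it appears only in the protocol synopsis, under efficacy in the treatment of breakthrough bleeds. Protocol 9.2.2 and SAP 5.7.2 give none. The general rule in SAP 5 (inferential statistics) declares significance at p below 0.050.

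**Other secondary endpoints** are descriptive (Protocol 9.2.2, SAP 5.7.2).

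**Analysis sets.** SAP 5: "The evaluation of the primary endpoint will be performed on the FAS (ITT analysis) and on the PP set (PP analysis"). Protocol 9.2.1 agrees. Neither says which set decides or whether both must succeed. For secondary efficacy variables, SAP 5.7.2 makes the FAS the base set and adds the PP set if the two differ by more than 5%.

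Neither document contains a testing order, a gatekeeping rule, an alpha split or any statement on multiplicity.

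**The concern.** The plan sets SABR and bleed success apart from the endpoints it treats descriptively, and gives each a formal hypothesis. The study is meant to support US approval in hemophilia A (Protocol 1.2 and 1.3), so it matters which results count as confirmed.

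Followed as written, either secondary claim can be called confirmed when TABR has not met its threshold. Each added test is another chance of a false confirmatory claim, and nothing limits the total. In addition, if the FAS and PP analyses of TABR disagree, the plan has no rule for the conclusion. PP membership depends on deviations classified case by case before database lock (SAP 3.3) in a study without blinding (Protocol 5.6), so the deciding set is better fixed in advance.

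**Working it through.** **1. The plan's own figure.** Protocol 9.1 and SAP 2.5 give power above 90% with n = 50, true mean 20, SD 15 and threshold 29.
- Standard error = 15/√50 = 2.121.
- Power = Φ(9/2.121 − 1.960) = Φ(2.283) = 98.9%. The noncentral t gives 98.6%.
- An exact Poisson test on 50 × 0.5 = 25 person-years rejects at 672 bleeds or fewer, against 29 × 25 = 725 expected. Its power is above 99.9%.

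The statement is reproduced. The documents give no error rate across the three tests.

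**2. Error across three tests at one-sided 2.5% each.** The level is stated for TABR, carried over by analogy for SABR, and taken from the protocol synopsis for bleed success.
- All three nulls true: upper bound 3 × 2.5% = 7.5%; if independent, 1 − 0.975³ = 7.3%.
- Only the two secondary nulls true: upper bound 2 × 2.5% = 5.0%; if independent, 1 − 0.975² = 4.9%.

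**3. Overlap of TABR and SABR.** Spontaneous bleeds are part of all bleeds, so these tests are positively correlated. With pure Poisson counts at the null values (an assumption), the correlation is √(19.1/29) = 0.81. P(TABR or SABR rejects) is 5% minus P(both reject). The bleed-success test is taken as independent of the counts (an assumption), so the three-test rate is 1 − (1 − u) × 0.975, where u is the rate for TABR or SABR.

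| TABR–SABR correlation | TABR or SABR (u) | All three tests |
|---|---|---|
| 0 | 4.9% | 7.3% |
| 0.81 (normal) | 3.9% | 6.3% |
| 0.81 (exact Poisson tests, 2,000,000 simulated trials) | 3.7% | 6.1% |
| 0.99 | 2.8% | 5.3% |

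**4. FAS and PP for the primary.** If success on either set counted, the TABR error alone would be 2.8% at an assumed FAS–PP correlation of 0.99 and 3.5% at 0.90. If both sets had to succeed, it would be at most 2.5%.

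**5. Effect of the remedies.**
- Fixed sequence at one-sided 2.5%: error across the claims at most 2.5% if each test is valid; TABR power stays at 98.9%.
- Equal split, 2.5%/3 = 0.833% each: same bound; TABR power 96.8% (normal) or 95.8% (t).

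**The case against.** The strongest reply is that the plan never claims a study-wide 2.5%. It states that level per test, has one primary endpoint, and calls its main approach descriptive (Protocol 9.2). In that overview it announces a formal test only for TABR. This stands in part: on one named set, the nominal level of the TABR test does not depend on what is tested afterwards. A reader might infer that the primary's 2.5% is compromised; the documents do not support that. The descriptive framing does not, however, cancel a test that both documents call confirmatory, nor one tied to the primary in every respect but its threshold.

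Three further readings go too far.
- **7.3% to 7.5% as the actual rate.** The first figure assumes independence and the second is a bound. TABR and SABR share their spontaneous bleeds, so about 6% is more realistic under Poisson counts.
- **FAS/PP testing as certain inflation.** No passage says that success on either set suffices. The FAS follows the intention-to-treat principle and is the base set for secondary efficacy variables. This is an ambiguity to close.
- **A 5% one-sided level for bleed success.** Applying the general p < 0.050 rule one-sided would raise the bound to 2.5% + 2.5% + 5% = 10%. The SAP does not say whether that p-value is one-sided, and the protocol synopsis gives 2.5%. One caution: the protocol at hand is version 03 of 16-Jan-2017, whereas SAP section 1 lists a version of 2017-09-07 that is not available here.

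It is also fair that bleed treatment is a separate objective from prophylaxis, so placing its test behind SABR is a choice and not a necessity.

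**Conclusion.** The point holds for the secondary claims. One secondary test is labelled confirmatory and another is confirmatory by analogy, with no rule linking either to the primary or to each other. At one-sided 2.5% per test, the chance of at least one false confirmatory claim is at most 7.5% with all three nulls true. It is about 6% at the Poisson-implied correlation of 0.81, and 5.3% at a correlation of 0.99. With only the two secondary nulls true it is at most 5%. The figures of about 6% and 5.3% assume that the bleed-success test is independent of the bleed counts.

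The missing alpha for bleed success in the SAP and the unnamed deciding set for TABR are gaps to close. The second adds error only under an either-set rule, which the plan does not state.

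All these figures take each test as valid at its nominal level. For the Poisson tests that is a separate question. If the planning SD of 15 also applied at a mean of 29 with half a year per patient (an assumption), the model standard error would be √(29/25) = 1.08 against 15/√50 = 2.12. The TABR test alone would then run at about 16%. Ordering the tests does not repair that.

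**What to change.** In SAP 5.7 and Protocol 9.2.2:

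1. State that the FAS analysis decides the primary endpoint and the PP analysis is supportive.
2. State one-sided 2.5% for the bleed-success test in the SAP.
3. Test in a fixed sequence, each at one-sided 2.5%: TABR against 29, then SABR against 19.1, then bleed success against 70%. This follows the endpoint order in Protocol 3.1. After the first non-rejection, report the remaining tests descriptively.

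An acceptable alternative to step 3 is to relabel SABR and bleed success as supportive, which removes the confirmatory claims.

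**Cost.** Wording changes in both documents. SAP 3.2 says no deviations from the protocol are planned, so a change made only in the SAP would have to be recorded there. No new data or patients are needed, and TABR power is unchanged. The price is that a later claim is lost if an earlier test fails. The plan gives an assumed effect for TABR but none for SABR, so the chance that SABR blocks the bleed-success claim cannot be stated from the documents.

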5.7.3 Exploratory Endpoint

An exploratory endpoint of this study is the descriptive efficacy of *Wilate* in surgical prophylaxis (for details see section 5.9).

5.8 Pharmacokinetics / Pharmacodynamics

For Pharmacokinetics and IVR assessments FVIII:C will be measured by both, the chromogenic (CHR) and one-stage assay (OS) and analyzed based on actual IMP potency.

The PK profiles of *Wilate* and the PK parameters derived from them will be summarized by descriptive statistics as well as the presentation of concentration vs. time plots based on the PK set. In the analysis of the PK profiles geometric means and standard deviations will be presented in addition to the arithmetic means and standard deviations.

The following PK parameter will be derived and presented using a non-compartment model:

- Area under the curve (AUC) and AUC normalized for the administered dose (AUC_{norm})
- FVIII in vivo half-life ($T_{1/2}$)
- Maximum plasma concentration (C_{max})
- Time to reach maximum plasma concentration (T_{max})
- Mean residence time (MRT)
- Volume of distribution (Vd)
- Clearance (CL)
- Incremental in vivo recovery (IVR)

Analysis of variance (ANOVA) will be used in an exploratory sense to assess a possible association between AB0 blood type, VWF:Ag, and the FVIII:C half-life of *Wilate*.

IVR will be analyzed for the FAS and additionally for the PP population if these populations differ by >5%. The results of the IVR assessments over time will be analyzed in summary tables for each time point and their differences to baseline along with 95% CIs for the mean differences.

To compare the pharmacokinetic characteristics of the 6-months PK-profile with those of the baseline PK-profile a matched-pairs sign rank test of the null hypothesis of no time difference will be performed at for all PK parameters.

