5.4 Dose and Dosing Schedule

5.4.1 PK Assessment Phases

In the 2 PK Assessment Phases performed in a subset of 20 patients before the start and after the end of the Prophylactic Treatment Phase, *Wilate* will be administered to all 20 patients as a single dose of 50 ± 5 IU/kg BW. Full vials should be used. The dose can be rounded to the next higher or lower full vial.

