5.4.2 Prophylactic Treatment Phase

In the Prophylactic Treatment Phase, *Wilate* should be administered every 2 to 3 days at a dose of 20–40 IU/kg BW for 6 months (+2 weeks) and at least 50 EDs.

In case of unacceptably frequent spontaneous breakthrough BEs (i.e., more than 2 spontaneous BEs or 1 major or life-threatening spontaneous BE within a 30-day period), the dose of *Wilate* should be increased by approximately 5 IU/kg (depending on the entire content of the additional vial(s) that need(s) to be reconstituted).

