5.4.3 Treatment of Breakthrough BEs

The dose (and duration) of treatment of BEs will depend on the location and extent of bleeding and on the clinical condition of the patient. The dose calculation is based on the empirical finding that 1 IU FVIII:C/kg BW raises the plasma level by 1.5–2.0% of normal activity. The recommended dose is determined using the following formula:

$$\text{Recommended units} = \text{body weight (kg)} \times \text{desired factor VIII rise (\%)} \text{ (IU/dL)} \times 0.5$$

In the case of the following hemorrhagic events, the factor VIII activity should not fall below the given plasma FVIII activity level (%) in the corresponding period. The following can be used to guide dosing in BEs:

- **Early hemarthrosis, muscle bleeding, or oral bleeding**
Target FVIII level: 20–40%
Recommended dose: 10–20 IU/kg
Repeat injection every 12–24 hours. At least 1 day, until the BE as indicated by pain has resolved or healing has been achieved.
- **More extensive hemarthrosis, muscle bleeding, or hematoma**
Target FVIII level: 30–60%
Recommended dose: 15–30 IU/kg
Repeat injection every 12–24 hours for 3 to 4 days or more until pain and disability have resolved.
- **Life-threatening hemorrhages**
Target FVIII level: 60–100%
Recommended dose: 30–50 IU/kg
Repeat injection every 8–24 hours until threat has resolved.

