6.1.1 Screening Visit

The following assessments will be performed during the Screening Visit:

- Obtaining voluntarily given, written (signed and dated) informed consent
- Inclusion and exclusion criteria
- Demographic characteristics
- Weight
- Height
- Medical history (including FVIII treatment during the last 6 months before screening)
- Vital signs

- Physical examination
- Routine safety laboratory
- Determination of CD4+ levels
- Determination of AB0 blood group (unless derived from medical history)
- Determination of FVIII inhibitors
- Hemophilia Joint Health Score (HJHS), unless obtained within 3 months before the Screening Visit
- Concomitant medications

Whenever possible, the interval between the Screening Visit and the PK or Non-PK Visit **should not exceed 30 days**. If the 30-day interval is exceeded, determination of the CD4+ count is to be repeated and must be $>200/\mu\text{L}$ for patients to be enrolled (i.e., exclusion criterion no. 4, see **Section 4.1.1**).

Any BEs occurring between the Screening Visit and the PK or Non-PK Visit should be treated with the patient's previously used FVIII concentrate. Similarly, prophylactic treatment between the Screening Visit and the PK or Non-PK Visit should be done with the patient's previously used FVIII concentrate.

After the Screening Visit,

- **patients undergoing PK assessment** will participate in PK Visit (see **Section 6.1.2**). The first prophylactic injection of *Wilate* after the PK Visit will mark the beginning of the Prophylactic Treatment Phase.
- **patients not undergoing PK assessment** will participate in the Non-PK Visit (see **Section 6.1.3**), during which the first prophylactic injection of *Wilate* will be administered. In this cohort, the first prophylactic injection of *Wilate* administered during the Non-PK Visit will mark the beginning of the Prophylactic Treatment Phase.

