6.1.2 PK Visit

Patients will receive *Wilate* at a dose of 50 ± 5 IU/kg (labelled dose) after a washout period of at least 72 hours from their last FVIII injection. Patients must not be experiencing any bleeding.

The following assessments will be performed:

- **Body weight** before injection
- Blood samples will be taken for the following purposes and at the following time points:
 - **FVIII:C plasma concentration (OS and CHR) for PK assessment** within 1 h before injection and 15 ± 5 min, 1 h (± 5 min), 3 h (± 15 min), 6 h (± 30 min), 9 ± 1 h, 24 ± 2 h, 30 ± 2 h, and 48 ± 2 h after the end of injection
 - **Safety laboratory** before and 48 ± 2 h after injection
 - **FVIII inhibitor** before injection
 - Plasma **VWF:Ag** and **VWF:Ac** within 1 h before injection and 15 ± 5 min after the end of injection
 - **Parvovirus B19 antibodies** before injection
 - **Retention sample** for possible additional virus marker testing before injection
- **Vital signs** before injection as well as 1 h (± 5 min) and 48 ± 2 h after injection
- **AE monitoring**
- **Concomitant medications**

At the end of this visit, patients will **receive a patient diary**. The Investigator will explain to the patient how to fill in the diary and emphasize the importance of carefully documenting all treatment details, AEs, and concomitant medications. Also, patients will be **provided with IMP** for home treatment. They will be re-supplied whenever necessary during the study.

The first prophylactic injection of *Wilate* after the PK Visit marks the beginning of the Prophylactic Treatment Phase.

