6.1.7 PK Study Completion Visit

The PK Study Completion Visit will take place 6 months (+2 weeks) after the start of the Prophylactic Treatment Phase.

Patients will receive *Wilate* at a dose of 50 ± 5 IU/kg (labelled dose) after a washout period of at least 48 hours from their last FVIII injection. Patients must not be experiencing any bleeding.

The following assessments will be performed:

- **Review of patient diary**
- **Body weight** before injection
- Blood samples will be taken for the following purposes and at the following time points:
 - **FVIII:C plasma concentration (OS and CHR) for PK assessment** within 1 h before injection and 15 ± 5 min, 1 h (± 5 min), 3 h (± 15 min), 6 h (± 30 min), 9 ± 1 h, 24 ± 2 h, 30 ± 2 h, and 48 ± 2 h after the end of injection
 - **Safety laboratory** before and 48 ± 2 h after injection
 - **FVIII inhibitor** before injection
 - Plasma **VWF:Ag** and **VWF:Ac** within 1 h before injection and 15 ± 5 min after the end of injection
- **Vital signs** before injection as well as 1 h (± 5 min) and 48 ± 2 h after injection
- **AE monitoring**
- **Concomitant medications**
- **Physical examination**
- **Parvovirus B19 antibodies** before injection, if first sample was negative

All used and unused IMP vials will be returned by the patient.

Patients prematurely withdrawing from the study for any reason will also be invited to attend the PK Study Completion Visit.

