8 APPENDICES

8.1 Formulas for derived variables

Variable	Description
Durations between two dates	Later date minus earlier date plus 1, expressed in days. (Remark: Duration will be 1, if both dates are the same.)
Annual bleeding rate	Number of bleedings under prophylaxis / time under prophylaxis (days)/365.25 (see prophylactic treatment phase)
AUC	Area under the curve from baseline to infinity $AUC = \sum \left(\frac{(C_n + C_{n+1})}{2} \cdot \Delta t \right) + \frac{C_{last}}{K}$ (C_{last} is the last available measurement)
AUC _{norm}	AUC normalized for the administered dose
AUMC	Area under the moment curve (from baseline to infinity) $AUMC = \sum \left(\frac{(t_n \cdot C_n + t_{n+1} \cdot C_{n+1})}{2} \cdot \Delta t \right) + \frac{C_{last}}{K^2} + \frac{t_{last} \cdot C_{last}}{K}$
CL	Clearance $CL = \frac{D}{AUC}$ where D is the actual dose administered (see remark above)
C_0	FVIII concentration before IMP administration
C_{max}	Maximal measured concentration after end of IMP infusion (peak concentration)
ED	Exposure day = each day the subject received IMP
Incremental recovery (IVR)	$IVR = \frac{(C_{max} - C_0) \cdot BW}{D}$

STATISTICAL ANALYSIS PLAN

Protocol No: WIL-27

Version Number: 5.0

Date of Issue: 2018-05-08

Page 26 of 27

	where BW stands for the body weight in kg and D is the dose according to the actual potency of the FVIII concentrate as described in above
MRT	Mean residence time $MRT = \frac{AUMC}{AUC}$
Prophylactic treatment phase	PK subgroup: (date of completion visit or date of last treatment with IMP in case completion visit not performed) – (date of first prophylactic treatment after the PK visit) Non-PK subgroup: (date of completion visit or date of last treatment with IMP in case completion visit not performed) – (date of first IMP infusion at Non-PK visit)
Success (for bleeding episodes and surgeries)	Excellent or good efficacy rating
T _{1/2}	In vivo half-life using linear regression on the terminal phase of the logarithm of the concentration; $T_{1/2} = \frac{\ln(2)}{K}$ (where K, the elimination rate constant, is determined as the slope of the regression line)
T _{max}	Time to reach maximum plasma concentration (Timing starts at end of infusion)
Vd	Volume of distribution $Vd = CL \cdot MRT$

STATISTICAL ANALYSIS PLAN Protocol No: WIL-27	
Version Number: 5.0 Date of Issue: 2018-05-08	Page 27 of 27

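### Unequal minimum washouts (72 h at baseline, 48 h at 6 months) and no pre-dose correction of AUC and Cmax can bias the SAP's paired PK comparison

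*SAP*

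**What the plan says.** The baseline PK dose is given "after a washout period of at least 72 hours from their last FVIII injection" (Protocol 6.1.2). The 6-month PK dose is given "after a washout period of at least 48 hours from their last FVIII injection" (Protocol 6.1.7). On both occasions Wilate "will be administered to all 20 patients as a single dose of 50 ± 5 IU/kg BW" (Protocol 5.4.1). I found no explanation of the different washouts.

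The FVIII given beforehand also differs. Up to the PK Visit, prophylaxis "should be done with the patient's previously used FVIII concentrate" (Protocol 6.1.1). During the study, Wilate "should be administered every 2 to 3 days at a dose of 20–40 IU/kg BW" (Protocol 5.4.2).

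SAP 8.1 defines AUC as "Area under the curve from baseline to infinity": trapezoids on the measured concentrations plus C_last/K. Cmax is the highest measured value. CL is dose divided by AUC, MRT is AUMC divided by AUC, and Vd is CL times MRT. The pre-dose level C0 is defined, but only the IVR formula uses it.

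SAP 5.8 then says: "To compare the pharmacokinetic characteristics of the 6-months PK-profile with those of the baseline PK-profile a matched-pairs sign rank test" will be done for all PK parameters. SAP 5 declares significance at p below 0.050.

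**The concern.** FVIII left over from the previous injection is counted as exposure from the PK dose. More is left after 48 h than after 72 h, so two profiles with identical true PK can differ, and the paired test takes that difference for a time effect. Protocol 1.4 itself expects FVIII to be measurable 48 h after 50 IU/kg in nearly all patients. Dosing every 2 to 3 days makes a gap near 48 h plausible at 6 months.

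PK at baseline and after 6 months is a secondary objective, and this is its only formal test. An apparent rise in exposure could be reported as a change over time, or could offset a true rise in clearance.

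**Working it through.** The documents state no power, effect size or variability for this comparison, so there is no plan figure to reproduce.

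**Inputs from the documents.** PK dose 50 IU/kg; prophylaxis 20–40 IU/kg; minimum washouts 72 h and 48 h; sampling at 0.25, 1, 3, 6, 9, 24, 30 and 48 h; 20 planned pairs. For recovery, Protocol 5.4.3 says that "1 IU FVIII:C/kg BW raises the plasma level by 1.5–2.0% of normal activity".

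**Assumptions.** Half-life T of 8–18 h, one compartment, the same T for all FVIII, steady-state dosing every 48 h before both visits, both washouts at their minima, and no true PK change.

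**Size of the shift.** Express the residual after washout w as a dose equivalent, for prior dose P:

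r(w) = P × 2^(−w/T) / (1 − 2^(−48/T))

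Post-dose concentrations are proportional to 50 + r(w), so the spurious 6-month/baseline ratio is

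R = (50 + r(48)) / (50 + r(72))

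Recovery cancels from R.

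For T = 12 h, 2^(−4) = 0.0625 and 2^(−6) = 0.015625, so r(48) = 0.0667P and r(72) = 0.0167P.
- P = 20: R = 51.333 / 50.333 = 1.020
- P = 40: R = 52.667 / 50.667 = 1.040
- P = 30 and recovery 2.0: C0 is 1.0% after 72 h and 4.0% after 48 h

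| Half-life (assumed) | R for P = 20 | R for P = 40 |
|---|---|---|
| 8 h | 1.006 | 1.011 |
| 12 h | 1.020 | 1.040 |
| 15 h | 1.032 | 1.063 |
| 18 h | 1.044 | 1.085 |

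Running the SAP 8.1 formulas at the protocol sampling times gives the same ratios for AUC and Cmax to within 0.1 percentage point. CL and Vd fall correspondingly: 2.0–3.8% for CL at 12 h. MRT moves by less than 0.05% (ratio 0.9996–0.9999), because AUMC and AUC scale together. IVR changes by less than 0.1%. T1/2 and Tmax do not move.

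**Direction under other conditions.**
- A patient with no residual at baseline (prior prophylaxis is not an entry criterion) gives R = (50 + r(48)) / 50. That is 1.027–1.053 at 12 h and 1.075–1.150 at 18 h.
- Suppose the earlier concentrate had an 18 h half-life and Wilate 12 h, with 30 IU/kg of each. Then r(72) = 2.225 and r(48) = 2.000, so R = 52.000 / 52.225 = 0.996, a slight reversal.
- Equal actual washouts, with everything else equal, give R = 1.

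**Effect on the test.** Two-sided signed-rank test, 20 pairs, normal paired log-differences centred on log R, 20,000 simulated samples per cell. Percentage of trials rejecting:

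| R | SD 0.10 | SD 0.20 | SD 0.28 |
|---|---|---|---|
| 1.00 | 5 | 5 | 5 |
| 1.01 | 7 | 5 | 5 |
| 1.02 | 13 | 7 | 6 |
| 1.04 | 37 | 13 | 9 |
| 1.06 | 67 | 22 | 13 |

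These SDs are assumptions. Since paired SD is about √2 times the within-patient SD, they correspond to a CV per occasion of roughly 7%, 14% and 20%.

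**After correction.** Subtracting C0·exp(−K·t) leaves a concentration proportional to 50·2^(−t/T) at both visits, so R = 1 and the test returns to its nominal level in this model.

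**The case against.** The strongest reply is that both washouts are minima. A patient dosed every 3 days may well have a 72 h gap at 6 months, and the asymmetry then largely disappears. The baseline residual comes from another concentrate of unknown dose and half-life. A reader might infer that the comparison is certainly biased toward higher exposure at 6 months; the documents support only a bias that is expected when actual washouts are near the minima. This part of the reply stands.

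It also stands that the effect is small at short half-lives, and that at a CV near 20% the test is barely disturbed (9% rejection at a ratio of 1.04).

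A reader might further infer that a developing inhibitor could go unnoticed. The plan does not rely on AUC for that. Inhibitor is measured centrally before the injection at the PK completion visit and at each other study visit, positive results are retested (Protocol 6.1.7 and 7.3.5.1), and IVR already subtracts C0.

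Finally, the listed PK endpoint is baseline PK only, and the protocol's PK analysis is descriptive. That limits the stakes, but it does not remove the reason to correct a formula that feeds a planned test.

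**Conclusion.** The point holds in conditional form. With washouts near their minima, AUC, AUCnorm and Cmax are overstated and CL and Vd understated at 6 months relative to baseline, by about 0.6–1.1% at a half-life of 8 h, 2.0–4.0% at 12 h and 4.4–8.5% at 18 h. The signed-rank test then exceeds 5%, from hardly at all at a ratio of 1.01 to 13–37% at 1.04 for paired log-SDs of 0.10–0.20. Half-life and variability are assumed throughout.

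Because MRT is AUMC divided by AUC, a reader might expect the residual to distort it too; it does not. MRT, T1/2, Tmax and IVR are essentially unaffected. The primary endpoint is untouched.

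One reservation applies to the washouts. SAP 1 cites a protocol dated 2017-09-07, while the supplied protocol is version 03 of 16-Jan-2017, so the later text may differ. The missing correction is in the SAP itself.

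**What to change.** In SAP 8.1:
- Subtract C0·exp(−K·t) from each post-dose concentration at both visits, with the pre-dose value set to zero, before computing AUC, AUCnorm and Cmax. Base CL and Vd on the corrected values.
- Compute AUMC from the same corrected concentrations, so that MRT stays consistent.
- Keep the measured Cmax in the IVR formula, which already subtracts C0; otherwise the residual is removed twice.
- Apply one pre-specified rule for C0 below quantification at both visits, with a sensitivity analysis (for example zero versus half the limit). Setting such values to zero could leave baseline uncorrected while 6 months is corrected, a smaller bias in the opposite direction.
- List actual washout times and C0 by visit, and keep the uncorrected comparison as a sensitivity analysis.

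The two washout passages should be reconciled or the difference explained; no washout rule is proposed here.

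The cost is a few lines of SAP text and code, since the pre-dose samples are already scheduled. Estimating K adds a little noise, and Wilate's K is only approximate for residual from the previous concentrate at baseline.
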